Potential participants are identified using medical chart and case review. The study eligibility requirements will be reviewed by the PI and study staff. The potential participant is pre-selected as tentatively meeting the eligibility requirements for the study. Research study staff will reach out to eligible patients through a phone call explaining the study. Randomization to the treatment (KRONOS postoperative brace) or control group (Hinged knee brace) will occur at the time of informed consent

Informed Consent Discussion

Investigator and/or PI and research study staff will contact the patient in clinic or via telephone to discuss the research study with them. Ideally, the informed consent discussion should be conducted when the study staff and potential participant has time to ask and answer questions. Information provided to the patient includes the rationale for the study procedure or treatment, the number of study visits and the study activities they will need to complete, risks involved, expected benefits, and alternatives to treatment.

The process may occur over a period of several discussions, culminating in the signing of a consent form in the office (Ipad or paper) or sent to their verified email address. The informed consent discussion will be documented in the patient profile or chart.

If the patient agrees to participate, their email addressed will be verified. The consent will be obtained electronically sent through the secured platform called Patient IQ to their email. The potential subject will then be prompted to reply with the appropriate passcode in order to access the consent form, and then provide the passcode again with their

Version 2.0: 4/25/2025 Page 4 of 11

signature (secured). No research activities will be performed prior to execution of the consent. A copy of the time stamped document will be sent to the study team through the electronic platform and a copy will be sent to the participant.

Study Design & Procedures-

This is a randomized controlled trial.

We estimate 40 participants (20 Kronos: 20 T-Scope) will be enrolled in the study.

Primary outcome variable

• Rates of extension deficit (as measured by the fraction of patients with reduced extension compared to the contralateral knee, determined by heel height and goniometric measurements of knee extension)

Bracing Protocol

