Both treatment groups will progress according to a standard of care postoperative rehabilitation program regardless of the group to which the patient is randomized.

KRONOS Bracing Group

Subjects randomized to the treatment group will be measured and fitted with the KRONOS knee brace at their initial clinic visit after study enrollment. The patient will be instructed to use the brace preoperatively and bring it to their surgery, after which the brace will be placed again on the patient postoperatively at the conclusion of their procedure. Subjects will be instructed to wear the brace until symmetric terminal extension is achieved as indicated by side-to-side comparison with the non-surgical limb. This will be under the supervision and approval of the providing physician. Subjects will be instructed to use the brace (locked in extension and under high tension) at night during sleep and ambulation, though removal for therapy and rehabilitation exercises will be permitted.

Control Group – Standard Breg T-Scope Postoperative Bracing

Subjects will be placed in a standard postoperative hinged knee brace in the operating room that will be locked in full extension. Subjects will be instructed to use the brace locked in extension while sleeping for 6 weeks and when ambulating until the patient is able to perform a straight leg raise with no extension lag outside of the brace, at which point the brace may be worn unlocked during ambulation.

Table 1. Study timeline.

Preop Surgery 2 6 weeks 12 6 months 12

Version 2.0: 4/25/2025 Page 5 of 11

			weeks		weeks		months
Patient Recruitment	•						
Informed Consent and Randomization Physical Exam (i.e. Heel height and	•						
goniometer measurement of active	•	•*	•	•	•	•	
extension, passive flexion, passive extension)							
Circumferential thigh							
measurement (including healthy	•		•	•	•	•	
knee at pre-op)							
Brace Placement	•**	•					
PROMs	•				•	•	•
Brace compliance survey	1 .	•**	•	•	.1	. 1	

^{*}Passive flexion and extension ROM only under anesthesia prior to beginning surgery

PROMs will include: IKDC, KOOS, VR-12, PROMIS Depression, PROMIS Physical Function, PROMIS Pain Interference, Return to Sport (RTS) and Return to Work (RTW), Resilience scale and brace compliance survey.

Study Interventions –

Prospective Data Collection

Timeline of Events

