- 1. Once subjects are indicated for ACL surgery, a review of inclusion criteria will be undertaken, and subjects will be offered the opportunity to participate in the study.
- 2. Pre-operative physical exam findings including Pivot-shift, Lachman, and range of motion data will be recorded.
- 3. Range of motion measurements (ROM), including heel height^{7,8} and goniometric measurements of 3 types of ROM (active extension, passive flexion, and passive extension) will be done at the initial visit, preoperatively on the day of surgery, *intraoperatively under anesthesia before the initiation of the surgery* (passive flexion and passive extension only), and at the designated postoperative timepoints indicated in Table 1 (1 week, 2 week, 6 week, 12 weeks, 6 months, and 12 months).
- 4. Thigh circumference will also be measured with tape measure at the mid-thigh and

Version 2.0: 4/25/2025 Page 6 of 11

^{**} Only for patients randomized to the KRONOS brace treatment group

suprapatellar levels on the operative knee as a surrogate for quadriceps atrophy, as previously done^{10–12}, pre-operatively and at the designated postoperative visits in Table 1 (1 week, 2 week, 6 week, 12 weeks, 6 months, and 12 months). Thigh circumference of the nonoperative healthy knee will also be measured pre-operatively for baseline comparison

- 5. Informed consent will be obtained. Prior to surgery (preoperative) subjects will be asked to complete standard of care patient reported outcomes questionnaires including IKDC, KOOS, PROMIS (Depression, Pain Interference, Physical function), VAS pain, VR/SF 12, RTS, RTW and brief resilience scale.
- 6. Brace compliance survey A survey assessing patient compliance with bracing instructions will be administered at the designated postoperative timepoints indicated in Table 1.
- 7. Subjects will proceed with operative management of their ACL tear, including appropriate treatment and documentation of concomitant injuries.
- 8. Subjects will be appropriately fitted for the brace corresponding to randomization on the day of surgery. All braces will be placed on the subject in the operating room at the conclusion of the procedure. All subjects will begin a standard of care physical therapy protocol on postoperative day 1-14.

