- 9. Subjects will undergo standard of care follow up at 1-week, 2-week, 6-weeks, 12-weeks, 6-months, and 12 months. At these standard of care visits, range of motion, including goniometric angle and heel-height measurements, will be made at all postoperative time points.

 Time-to-achievement of full symmetric extension relative to the non-surgical knee will be monitor and recorded. Additional physical exam of the knee will be performed at all follow-up time points.
- 10. At 12 weeks, 6 months, and 12 months, subjects will also be asked to complete standard of care patient reported outcomes questionnaires including IKDC, KOOS, PROMIS, VAS pain, VR/SF 12, and brief resilience scale. Subjects will also be asked to answer standard of care questions regarding return to work and return to sport throughout the 1-year postoperative period.

Retrospective Data Collection

The following data will be abstracted from secured electronic medical record databases (Epic, Athena, Opal, Patient IQ) and electronically recorded on coded data collection tool for this study:

- Demographic information (age, sex, body mass indes (BMI), laterality)
- Chief Complaint
- History of present illness

Version 2.0: 4/25/2025 Page 7 of 11

Physical Exam

Opal and Joints will be used to capture the following:

Surgical approach

Arthroscopic diagnoses

Techniques used

Fixation device / technique

Preoperative imaging including but not limited to MRI

The following outcome variables will be taken from Athena and Patient IQ:

- Postoperative complications
- Failure of primary reconstruction
- Need for a revision or subsequent procedure
- Preoperative / postoperative patient reported outcomes (PRO) including:

IKDC, KOOS, VR-12, PROMIS Depression, PROMIS Physical Function, PROMIS

Pain Interference, Return to Sport (RTS) and Return to Work (RTW), Resilience scale

Other outcomes variables of interest:

- Time-to-achievement of full extension
- Degree of extension loss
- Time to walking without a limp
- Quad circumference difference
- Frequency of brace use
- Number of postoperative physical therapy visits up to one year post-op
- Standard of care Breg T-scope group: time to unlocking the brace
- Kronos group: time to no quad assist (no dial engaged)

Rehabilitation Protocol

The rehabilitation program will be started on the day after surgery according to the providing physician's standard protocol.

Risk/benefit assessment –

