The statistical software *R* will be used for analyses and calculation of relevant p-values, standard deviation, correlation coefficients, and confidence intervals. Categorical variables will be analyzed via Chi-squared test, while quantitative variables will be analyzed via students' t-test for parametric data and Wilcoxon Mann-Whitney test for nonparametric data.

Data & Safety monitoring

Version 2.0: 4/25/2025

There is minimal risk to the subjects except the potential for loss of privacy and confidentiality, but every reasonable effort will be made to protect the patient's information while their data is used as part of this study.

Data storage & confidentiality –

Participant information will be collected and maintained in a excel data sheet housed on the Midwest Orthopedics at Rush (MOR) server, which is dual-factor authentication protected and accessible only to research staff. Subjects identity will be coded via the use of a separate document key (electronic excel spreadsheet) correlating subjects' Rush medical record numbers with a study ID assigned for the sole purpose of this study. This key electronic document will be maintained as a separate electronic file (excel spreadsheet) from data collection tool and will be housed in the Midwest Orthopaedics at Rush server, which is dual-factor authentication protected and accessible only to research staff.

Files will not be shared with non-study personnel.

According to (Rush policy OP-0432 and CC-G04) and study data must be maintained for 10 years in accordance with Illinois State Law. After this time the data will be destroyed by permanently and securely deleting electronic files on the Master key document (PHI) and the coded data collection tool.

References:

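### The questionnaire scores are to be compared by unadjusted tests although preoperative scores are collected; a prespecified baseline-adjusted model would gain precision if the pre-post correlation exceeds about 0.17 to 0.19

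*Protocol*

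**What the plan says.** The Data Analysis and Statistical Considerations section gives one rule for all quantitative outcomes: "quantitative variables will be analyzed via students' t-test for parametric data", and the Wilcoxon Mann-Whitney test for nonparametric data. It mentions no covariate or regression model, and it does not say whether follow-up values or changes are to be compared.

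The preoperative values exist. Under Timeline of Events, item 5, before surgery "subjects will be asked to complete standard of care patient reported outcomes questionnaires including IKDC, KOOS", together with PROMIS, VAS pain and VR/SF 12. Item 10 repeats them: "At 12 weeks, 6 months, and 12 months, subjects will also be asked to complete standard of care patient reported outcomes questionnaires". Item 4 measures operative-limb thigh circumference before surgery and at the postoperative visits, and adds: "Thigh circumference of the nonoperative healthy knee will also be measured pre-operatively for baseline comparison". The corresponding entry under Other outcomes variables of interest is only "Quad circumference difference".

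The timing of these values matters. The Consent process section states: "Randomization to the treatment (KRONOS postoperative brace) or control group (Hinged knee brace) will occur at the time of informed consent". Under KRONOS Bracing Group, patients "will be measured and fitted with the KRONOS knee brace at their initial clinic visit after study enrollment" and are told to use the brace before surgery. Timeline item 8 instead places fitting on the day of surgery. Item 3 says that range-of-motion measurements "will be done at the initial visit, preoperatively on the day of surgery", and again under anaesthesia.

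**The concern.** A patient's preoperative score usually carries some information about the later score. A two-sample test of follow-up values ignores it and leaves that between-patient variation in the error term. The trial enrols 40 patients and may analyse as few as 32 if the allowance for loss to follow-up is used up. It is sized only for the binary primary outcome, so the quantitative outcomes have no power allowance of their own. At stake is the width of the confidence intervals for the secondary patient-reported outcomes, and whether an adjusted analysis is fixed in advance or added after the data are seen.

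**Working it through.** **The plan's own figure.** The protocol's 32 patients (16 per arm) come from the primary-outcome rates 0.545 and 0.091, alpha 0.05 and power 80%. The two-sided normal-approximation formula with pooled variance gives n = [1.96·√(2·0.318·0.682) + 0.8416·√(0.545·0.455 + 0.091·0.909)]² / 0.454² = 15.3, rounded up to 16 per arm. The size reproduces, but it concerns the binary outcome and has no bearing on the quantitative ones.

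**Inputs.** From the protocol: N = 40 (20 per arm), or N = 32 (16 per arm) after losses; alpha 0.05. Assumed, because the protocol gives no SD or correlation: normal errors, two-sided testing, a true difference of 0.8 SD, and r from 0 to 0.7.

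**Break-even correlation.** The expected variance of the adjusted difference, relative to the unadjusted difference in follow-up values and including the cost of estimating the slope, is

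(1 − r²)(N − 3)/(N − 4).

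This equals 1 at r = √(1/(N − 3)), which is √(1/37) = 0.164 at N = 40 and √(1/29) = 0.186 at N = 32. On the power scale, with the lost degree of freedom counted, the break-even is 0.167 and 0.188.

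**Power and detectable difference.** Unadjusted: noncentral t with N − 2 degrees of freedom. Adjusted: noncentral t with N − 3 degrees of freedom, averaged over chance baseline imbalance.

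| | Unadjusted | r = 0 | r = 0.3 | r = 0.5 | r = 0.7 |
|---|---|---|---|---|---|
| Power at 0.8 SD, 20 per arm | 0.693 | 0.681 | 0.722 | 0.801 | 0.925 |
| Power at 0.8 SD, 16 per arm | 0.591 | 0.576 | 0.616 | 0.700 | 0.853 |
| SD detectable with 80% power, 20 per arm | 0.909 | 0.922 | 0.880 | 0.799 | 0.659 |
| SD detectable with 80% power, 16 per arm | 1.024 | 1.043 | 0.995 | 0.903 | 0.745 |

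The worst case, r = 0, costs 0.693 − 0.681 = 1.2 points at 20 per arm and 0.591 − 0.576 = 1.5 points at 16 per arm. At r = 0.5 the gain is about 11 points at either size.

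**If changes are tested.** Relative to the raw comparison, a change score has variance 1 + k² − 2rk, where k is the preoperative SD divided by the postoperative SD. It is less precise than the raw comparison when r < k/2, which is r < 0.5 with equal SDs. With equal SDs, the variance of the adjusted analysis relative to the change score is

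(1 + r)/2 × (N − 3)/(N − 4).

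This is below 1 when r < (N − 5)/(N − 3): 27/29 = 0.93 at N = 32 and 35/37 = 0.95 at N = 40. Above that, the loss of variance is at most 29/28, or 3.6%, at N = 32 and 37/36, or 2.8%, at N = 40.

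**Extension loss.** Values may cluster at zero, so the normal model is doubtful. An illustrative simulation at 20 per arm used loss floored at zero, an assumed SD of 3 degrees, the protocol's control rate of 0.545 and an assumed effect of 60% of the latent gap between the two protocol rates. Wilcoxon power was about 70% throughout. Adjustment on raw values gave 68%, 70%, 77% and 89% at r = 0, 0.3, 0.5 and 0.7, so there was no gain up to r = 0.3.

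**The case against.** The strongest case against is that nothing here is an error. The planned tests are valid, the outcomes are secondary, the protocol gives no r, and covariates are commonly left to a statistical analysis plan. Nothing in the protocol supports r of 0.5 or 0.7 between scores taken with an acute tear and scores taken 12 weeks to 12 months after reconstruction. For r between 0 and 0.3, the change in power at 20 per arm is only −1.2 to +2.9 points. All of that stands as a limit on size. It does not remove the point, because the protocol itself assigns the test to every quantitative variable; an analysis plan that adjusted would depart from it.

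The second objection is about the covariate. Randomization is at consent, item 5 lists consent before the questionnaires, and KRONOS patients are told to wear the brace before surgery. As sequenced, a preoperative value could follow disclosure of the assignment, and even brace wear in one arm. Adjusting for a value affected by assignment can bias the comparison, a risk the unadjusted follow-up comparison does not carry. This stands, and is why the timing of the covariate is a precondition of the fix.

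The third objection is that a reader might carry the threshold of about 0.2 straight over to thigh circumference. The protocol does not support that: its listed outcome is an undefined difference. The threshold holds for a raw or between-limb comparison, where r is the correlation between the matching preoperative and postoperative quantities, but not for change from preoperative.

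**Conclusion.** The point holds as a modest gain in efficiency for the questionnaire scores. It depends on r exceeding about 0.17 at 20 per arm or 0.19 at 16 per arm. Under the assumed 0.8 SD difference, adjustment does between 1.2 points of power worse (r = 0) and about 23 points better (r = 0.7) at 20 per arm. The upper figure shows the range and is not a forecast.

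A reader might infer that the planned tests are wrong or that the trial's main conclusion is at risk. Neither follows: an unadjusted randomized comparison is valid, and the binary primary outcome and its sample size are not involved. Outcomes with no preoperative value are also outside the point. Nor does the material justify replacing the planned test for degree of extension loss, where the gain is uncertain and rests on an invented distribution.

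**What to change.** - **Questionnaire scores.** In the Data Analysis section, prespecify for IKDC, KOOS, PROMIS, VAS pain and VR-12 a linear model of the postoperative score on arm plus the patient's own preoperative score, with the unadjusted test as a sensitivity analysis.
- **Precondition on timing.** State that the covariate is recorded before any KRONOS wear and, where possible, before the patient learns the assignment. Exclude day-of-surgery and under-anaesthesia values as covariates. The KRONOS Bracing Group section and Timeline item 8 disagree on when the brace is fitted and must be reconciled, so that the pre-brace value can be identified.
- **Thigh circumference.** First define the listed difference as between limbs or from preoperative. Then adjust for the matching preoperative value.
- **Degree of extension loss.** Leave the planned test as primary and report a baseline-adjusted estimate alongside as supportive.

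The cost is a few sentences of analysis text, one degree of freedom per model, at most 1.2 points of power (20 per arm) or 1.5 points (16 per arm) if r is near zero, and attention to when the preoperative value is recorded. No new measurement is needed. The change should be made before outcome data are examined by arm.

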We hypothesize that subjects randomized to receive the KRONOS postoperative unloader knee brace will reach full extension sooner and have reduce extension deficits compared to subjects randomized to receive the standard Breg T-scope hinged brace. In addition, it is hypothesized that the KRONOS subjects will require fewer additional treatments for extensions deficits including, but not limited to, additional therapy, intra-articular injections, oral corticosteroids, manipulation under anesthesia, or arthroscopic revision surgery.

Selection of Subjects –

Patients scheduled to undergo primary ACL reconstruction as indicated via CPT 29888 from the Athena electronic medical record (EMR) will be identified and eligible for enrollment in this study. Following the informed consent process outlined below, we will prospectively enroll and randomize 20 participants to one of the two study arms (KRONOS versus Breg T-scope post-operative knee brace), totaling 40 participants in each group.

Inclusion Criteria:

- Subjects > 18 years of age
- English-speaking
- Scheduled to undergo primary anterior cruciate ligament reconstruction surgery
- No history of prior knee surgery on the operative knee
- No concomitant ligamentous repair or reconstruction procedures (i.e. ligamentous pathology aside from anterior cruciate ligament).
- Subjects undergoing concurrent partial meniscectomy or meniscus repair that would not alter postoperative weight-bearing status or rehabilitation protocol would be eligible for inclusion.

Version 2.0: 4/25/2025 Page 3 of 11

• Clinical and radiographic examination (MRI) consistent with an acute full thickness ACL tear

Exclusion Criteria:

- Age < 18 years of age
- Non-English speaking
- Revision ACL reconstruction
- Multi-ligamentous injury, including concomitant posterior cruciate ligament, medial collateral ligament and fibular collateral ligament injuries
- Concomitant meniscal or cartilage injury that would alter postoperative weight bearing status or rehabilitation protocol
- Inability to comply with the proposed follow-up clinic visits
- Subjects lacking decisional capacity
- Worker's compensation subjects
- Requiring a custom-sized brace

Consent process -

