There is no direct benefit to the patient for his/her participation in this study.

The results will contribute to the optimization postoperative bracing and rehabilitation protocols following ACL surgery. This study will help determine if the KRONOS postoperative knee brace is an efficacious and safe methodology to improve range of motion and reduce extension deficits following ACL reconstruction.

Version 2.0: 4/25/2025 Page 8 of 11

Potential risk may include having the participant's privacy or confidentiality compromised. The participant's identities will not be identifiable in publications resulting from this investigation. Every reasonable effort will be made to protect the participant's information while their data is used as part of this study.

The alternative to participation in this study is not to participate.

Costs to the subject—

A brace will be provided to each study participant free of cost regardless of what group they are in—a standard of care Breg T-Scope brace or a Kronos brace.

No insurance coverage will be offered for regularly scheduled standard of care postoperative visits. However, any additional visits scheduled solely for the purpose of this study will be covered at no cost to the patient.

Compensation of subjects-

No compensation will be offered to study participants.

Data Analysis and Statistical Considerations -

Power analysis was based on data published by Mikkelsen et al.⁶ as part of an ACLR randomized controlled trial of a hyperextension brace. A priori power analysis was conducted to determine the sample size required to detect a significant difference in the proportion of patients experiencing a loss of full knee extension of $\geq 2^{\circ}$ between the straight brace and hyperextension brace groups. Using the observed proportions from the study (p1=0.545 for the extension group and p2=0.091 for the hyperextension group), the following parameters were used in G*Power for the calculation: **Statistical test**: Fisher's exact test (two independent groups); **Effect size**: w=0.57; **Significance level** (α): 0.05; **Power** ($1-\beta$): 0.8. The analysis indicated that a total sample size of 32 **participants** (16 per group) would be required to achieve 80% power to detect a statistically significant difference in the proportions of patients experiencing knee extension loss at $\alpha=0.05$. To account for potential loss of subjects to follow-up, a total of 40 subjects will be eligible to be enrolled.

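### Time to full extension and time to limp-free walking fall under a t-test/Wilcoxon rule that cannot properly handle patients who never reach the milestone or are lost before it

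*Protocol*

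**What the plan says.** The Hypothesis section states that KRONOS patients "will reach full extension sooner and have reduce extension deficits". Under Timeline of Events, item 9 adds: "Time-to-achievement of full symmetric extension relative to the non-surgical knee will be monitor and recorded". The list of other outcome variables repeats time to full extension and adds "Time to walking without a limp". It also holds two brace milestones, each defined in one arm only: "Standard of care Breg T-scope group: time to unlocking the brace", and time to no quad assist in the KRONOS arm.

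The tests are set in Data Analysis and Statistical Considerations. For categorical outcomes: "Categorical variables will be analyzed via Chi-squared test". For all quantitative outcomes, the rule is a "t-test for parametric data and Wilcoxon Mann-Whitney test for nonparametric data". No other test is named for comparing the arms on any outcome. The protocol mentions no Kaplan-Meier, log-rank or Cox analysis, and gives no rule for a patient who has not reached a milestone.

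The same section expects incomplete follow-up: "To account for potential loss of subjects to follow-up, a total of 40 subjects will be eligible to be enrolled". Items 3 and 9 of the Timeline of Events place range-of-motion visits at 1, 2, 6 and 12 weeks and at 6 and 12 months.

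**The concern.** A time to a milestone is quantitative, so the stated rule reaches it, and no other rule does. Both named tests need one value per patient. Two kinds of patient do not have one: those still short of full extension (or still limping) at the last visit, and those lost before reaching the milestone.

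With no rule for them, the easiest course is to compare only the patients with a recorded time. That group is selected after randomisation by the outcome itself. If one brace brings slow patients to full extension late, it adds long times to its own arm, while the same patients in the other arm drop out of the comparison. The better brace can then look no different, or slower. At stake is the test of the first clause of the hypothesis.

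**Working it through.** **The plan's own figure.** The protocol gives no power figure for the time outcomes. Its only calculation is for the binary outcome, with p1 = 0.545, p2 = 0.091, alpha 0.05 and power 0.80. By the pooled two-proportion formula, with mean proportion 0.318:

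n = [1.96·√(2·0.318·0.682) + 0.842·√(0.545·0.455 + 0.091·0.909)]² / 0.454² = (1.291 + 0.484)² / 0.206 ≈ 15.3, so 16 per arm and 32 in all.

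Then 32 / (1 − 0.20) = 40, an implied loss of 20%. None of this bears on the time outcomes.

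**Inputs from the protocol.** 20 per arm, visits at 1, 2, 6, 12, 26 and 52 weeks, and loss expected.

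**Assumptions.** Never-achieve shares, speed among achievers and dropout are not in the protocol. Times among achievers are exponential with a control median of 4, 6 or 9 weeks. Dropout is 10% or 20%, uniform over 52 weeks and unrelated to the milestone. Each setting has 2,000 simulated trials, and ranges span the medians and dropout rates. Worst-rank Wilcoxon puts 12-month non-achievers at a tied worst rank and leaves dropouts out. Log-rank uses all randomised patients.

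| Scenario (control vs KRONOS) | Achievers-only Wilcoxon | Achievers-only t-test | Worst-rank Wilcoxon | Log-rank |
|---|---|---|---|---|
| (a) Never achieve 54.5% vs 9.1%, equal speed | 4-5% | 4-5% | 59-69% | 78-85% |
| (b) Never achieve 25% vs 5%, hazard ratio 1.5 among achievers | 13-15% | 15-18% | 38-43% | 53-56% |
| (c) All achieve eventually, hazard ratio 2 | 37-44% | 41-48% | 38-44% | 49-51% |
| (d) Never achieve 10% vs 2%, equal speed | 4-5% | 5% | 5-6% | 8-11% |

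With 20% never achieving in both arms and equal speed, every test rejects in about 4-6% of trials.

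Scenario (a) borrows the planning rates. The protocol gives those for extension loss of at least 2 degrees at an unstated time, not for never reaching full extension. The achievers-only result there follows by reasoning: once non-achievers are removed, the arms have the same distribution of times, so the test can reject only at its nominal level. About 20 × 0.545 = 10.9 control patients are left out. On KRONOS it is 20 × 0.091 = 1.8, or 2-3 with dropout.

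**Can the direction reverse?** Scenario (e) assumes these cumulative shares at full extension:

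| Week | 1 | 2 | 6 | 12 | 26 | 52 |
|---|---|---|---|---|---|---|
| Control | 10% | 25% | 45% | 55% | 60% | 60% |
| KRONOS | 10% | 25% | 45% | 60% | 80% | 90% |

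KRONOS is never worse. The achievers-only means without dropout are:

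- Control: (10·1 + 15·2 + 20·6 + 10·12 + 5·26) / 60 = 410/60 = 6.8 weeks.
- KRONOS: (10·1 + 15·2 + 20·6 + 15·12 + 20·26 + 10·52) / 90 = 1380/90 = 15.3 weeks.

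The better arm looks 8.5 weeks slower (about 8 with dropout). In 3,000 trials per setting, achievers-only Wilcoxon is significant against KRONOS in 22-26%. Log-rank is significant in its favour in 23-27%.

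**Entering the last visit as the event time.** This is another way to force a value. With no true difference, a 12-week median, 10% never achieving and loss of 5% vs 35%, the type I error is 0.10 (t-test) and 0.09 (Wilcoxon). With loss of 5% vs 50% it is 0.18 and 0.14. Log-rank stays at 0.05 in both.

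**The case against.** The strongest objection is that the test rule is generic and names no time outcome, and that handling of non-achievers and dropouts is commonly left to an analysis plan, which is not at hand. The protocol nowhere says that non-achievers are dropped, and a Wilcoxon test with non-achievers ranked worst is compatible with its text. This has weight on the missing detail. It does not clear the rule, because the protocol assigns tests to all quantitative variables and offers nothing else. A log-rank test in an analysis plan would depart from it.

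Several narrower points stand:

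- Worst-rank Wilcoxon removes the reversal in (e): it is significant against KRONOS in under 1% of trials. It still loses power there, favouring KRONOS in 9-12% of trials against 24-29% for log-rank, at 0-20% dropout.
- Scenario (e) was built with a late benefit only. The hazards are not proportional, so a single hazard ratio would summarise it poorly.
- Table 1, as it can be read, shows no physical-examination mark at 12 months, although items 3 and 9 of the Timeline of Events state 12-month range-of-motion visits. If extension were read only to 6 months, the reversal would fall to about 14-16% and log-rank power in (e) to about 13%.
- Limp has no row of its own in Table 1, so its assessment times need to be clear before censoring at the last assessment has a meaning.
- Both outcomes are non-primary, and at 20 per arm power is modest under any method.

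**Conclusion.** The concern holds. The only stated rule gives two censored outcomes to tests that need a complete value for every patient, and one of those outcomes carries the first clause of the hypothesis. The size of the loss depends on how many patients never reach the milestone and on what is done with them. Against an achievers-only Wilcoxon test, log-rank gains between about 4 points (scenario d) and about 80 points (scenario a). Against a worst-rank Wilcoxon test, the gain in (a) to (d) is from a few points to about 20. A reversed direction is possible only under some handlings, achievers-only being the one shown. All these figures rest on assumed shares, speeds and dropout, and on dropout unrelated to the milestone. The binary primary outcome and the sample size are untouched. The change should be made, but the trial does not depend on it.

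**What to change.** In Data Analysis and Statistical Considerations, take the two between-arm time outcomes out of the t-test/Wilcoxon rule and state the following:

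- Time to full extension and time to limp-free walking are analysed in all randomised patients, with Kaplan-Meier curves and a log-rank test or Cox model. An interval-censored or discrete-time version is preferable because extension is read at visits.
- Patients who have not reached the milestone are censored at their last assessment of it.
- A hazard ratio with its confidence interval is reported beside the curves, which also show any departure from proportional hazards.
- The two single-arm brace milestones are described by Kaplan-Meier only, with no between-arm test, since each is a different event.
- The t-test and Wilcoxon test stay for quantitative outcomes observed in full.

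Table 1 should also be checked against the Timeline of Events on the 12-month examination, and the visits at which limp is assessed should be stated.

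The cost is one or two sentences on the analysis, using standard R functions. No new patients or visits are needed, and for extension no new data.
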